**3. Request for Revisions**

A. Did IRB staff specifically request that you submit this amendment?

Yes  No

B. Is this protocol a Cancer Center protocol (involve the study of cancer)?

Yes  No

i. If yes, provide the date the amendment was approved by the Protocol Review Committee of the Cancer Center.

C. Is this protocol a General Clinical Research Center protocol?

Yes  No

*If yes, make sure that you have submitted this amendment to that Committee as well.*

D. Check all that are applicable, explain in E. below, and attach supporting documentation.

Scientific Changes to Protocol  
 Eligibility/Ineligibility Criteria Changes

Change in Study Title  
 Changes to Consent Form (may affect currently approved HIPAA authorization)

Change in Protocol Procedures

Changes to Information Sheet or other previously approved materials given to subjects for information purposes

Change Requiring Re-consent (HIPAA authorization may be necessary)

Editorial Changes in HIPAA authorization (may occur when consent is revised)

Study Suspension

Closure to Accrual (e.g. interventions and/ or follow-up still occurring locally)

Addition or change to surveys, questionnaires, etc.

Change in Sponsor (contact the office if you have a new or additional sponsor)

Change in Compensation

Change in Collaborating Sites (may need agreement, see manual guidance.)

Increase in Accrual Target to:

Request for Review of Recruitment Materials

Other – Describe below in E.

Request for Review of Retention Materials  
 Request to share data/specimens with another institution (agreements may be required)

**E. Provide a description and justification for the requested change(s) listed in Section C. above.**

Research Protections Office, [name], [contact]

**Changes in Protocol Procedures:** Although the survey questions have been drafted using previously validated surveys, due to necessary modifications, we believe we should test the reproducibility of this study. To do so, we will administer the survey via telephone to twenty participants one day after the initial administration of the survey (which they will complete in the waiting room, as all other participants will do). We will use this information to confirm that the results of the study are reproducible.

**Survey Changes:** We have added age, socioeconomic status, and sex to the survey. We believe that the demographic information may affect the levels of satisfaction and anxiety of the family members, and this would be valuable information to obtain. In addition, University of Vermont Medical Center has launched a new website that allows family members to track their family members during the perioperative period. Access to this website may affect the levels of anxiety. We have added a question to the survey asking if they were aware of this website, and if so, if they made use of it.

## F. Grant Funding Changes

The IRB has the following regulatory mandate:

*"Department of Health and Human Services (HHS) regulations at 45 CFR 46.103(f) require that each application or proposal for HHS-supported human subject research be reviewed and approved by the Institutional Review Board."*

To meet this mandate, the IRB has to be made aware of when originally pending (including JIT) grants have subsequently been awarded or when supplements have been awarded. This gives us the opportunity to review the subsequent version of the grant in respect to the currently approved protocol. It is at this point that you need to revise your consent, if applicable, to include the new sponsor.

### Check the Appropriate Funding Change Below

Resubmission of Grant that was not previously funded (Note: If this is a new competing grant or a renewal, an amendment is not appropriate, a new protocol is required.)

Original Grant has now been funded

Supplemental Grant funding has been received

If any of the options above are checked, provide the specific grant information below.

InfoEd Proposal #

Grant # (full number including the version # related to the submission)

Is this new grant identical to the originally approved grant/protocol.  Yes  No

If yes, skip to #10 below. If no, explain the changes below and formally request an amendment to the protocol by completing this form. (Note: Now is when you would need to revise your consent, if applicable, to include the new sponsor.)

Confirm that the new corresponding grant is attached to this submission.  Confirmed

### Grant Funding has ended

Do you wish to close the protocol?  Yes  No

If yes, you must submit a continuing review form.

If no, and you are still using a consent, you must remove the reference to the old sponsor and put in the new one. List below the new sponsor.

## G. Supporting sponsor documentation for this amendment is attached. Confirm by checking here.

### 4. Is this change being submitted as a result of safety information already submitted to the IRB?

Yes  No

If yes, provide the date of the safety information and a brief description of the safety information: (example: IDB submitted on 1/1/2001 with increased risk of seizures)

**Family Member Demographic Information**

Age: \_\_\_\_\_

Sex (circle one): F / M / Other

Highest educational degree you have attained (check one):  High School diploma or equivalent (GED)  
 Associate degree  
 Vocational degree  
 Bachelor's degree  
 Master's degree  
 Professional degree  
 None of the above

1. How are you related to the patient (i.e parent, spouse, partner, son, daughter, etc)?

2. Please rate your level of satisfaction with your overall experience today in the perioperative area by circling the answer that best describes your satisfaction (with 1 being extremely unsatisfied and 5 being extremely satisfied).

|             |               |              |                 |               |                |
|-------------|---------------|--------------|-----------------|---------------|----------------|
| None at all | Extremely low | Somewhat low | Not high or low | Somewhat high | Extremely high |
| 0           | 1             | 2            | 3               | 4             | 5              |

3. Please rate your level of anxiety during the surgery by circling the answer that best describes your anxiety (with 0 being none at all and 5 being extremely high).

|             |               |              |                 |               |                |
|-------------|---------------|--------------|-----------------|---------------|----------------|
| None at all | Extremely low | Somewhat low | Not high or low | Somewhat high | Extremely high |
| 0           | 1             | 2            | 3               | 4             | 5              |

4. Please rate your level of satisfaction with the number of updates provided during the perioperative period (with 1 being extremely unsatisfied and 5 being extremely satisfied).

|             |               |              |                 |               |                |
|-------------|---------------|--------------|-----------------|---------------|----------------|
| None at all | Extremely low | Somewhat low | Not high or low | Somewhat high | Extremely high |
| 0           | 1             | 2            | 3               | 4             | 5              |

5. Please check all that apply regarding the frequency of updates you received during the perioperative period.

Updates were too frequent  
 Updates were too infrequent  
 I was satisfied with the number of updates I received

6. In an ideal scenario, at which time points during surgery would you like to be updated? (Check all that apply)

Patient is entering the OR  
 Initial skin incision has been made  
 Critical part of the case is complete, and closure is about to begin  
 Closure is complete, and patient will be transferred to the recovery room when ready  
 Patient is leaving the OR

7. Please check all that apply regarding the amount of detail in the updates you received during the perioperative period.

- Updates were too detailed
- Updates were lacking enough detail
- I was satisfied with the amount of detail in the updates

8. In your opinion, what would be the ideal method to deliver updates to family members during surgery?

- Human communication
- Text message
- Pager
- Application for electronic device (cell phone, tablet, etc.)
- Television Screen in the Waiting Room

9. At what point during the perioperative period would you prefer to have a consult with the surgeon? Please select one answer.

- Critical part of the case is complete, and closure is about to begin
- Closure is complete
- Upon transfer to the recovery room

10. Were you aware the University of Vermont Medical Center has a new website that allows family members to track the status of their loved one in the OR?

- Yes

*If yes, did you utilize this website (circle one): Yes / No*

- No

11. Please feel free to provide any feedback and/or suggestions regarding the communication with family members during the perioperative period.

---

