This will be a survey-based study. On the day of the surgery, a research team member will inform the patient and family that a study is being conducted to investigate the effect of perioperative communications on family satisfaction and anxiety. It will be explained that each family will randomly be assigned to two communication pathways, and there will be a short survey for them to complete post-surgery. In the control pathway, the surgeon will communicate with the family per his/her usual practice near the completion of the surgical procedure. In the intervention group, the families will receive additional standardized electronic updates via pagers at three pivotal moments: 1) Initial skin incision has been made, 2) Critical part of the case is completed and closure has begun, 3) Closure is complete, and patient is about to be transferred to the recovery room. Then, the surgeon will communicate the final update near the end of the surgical procedure per his/her usual practice.

After the surgery is complete, and both control and intervention groups have received the final update, a research team member will locate the waiting family and administer the post-operative survey rating their satisfaction and anxiety levels using Likert scale questions (1-5 scale). In addition to the survey, basic demographic information of the patient and family member completing the survey, as well

as the number of people in the waiting party, will be reported.

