Prior to the surgery, a member of the research team will review each case to determine if the surgery meets study criteria. The exclusion criteria include: surgeries lasting less than two hours, patients under the age of 18, non-speaking patients and/or families, or patients that do not have family members present in the pre-operation area. On the day of the surgery, a research team member will inform the patient and family that a study is being conducted to investigate the effect of perioperative communications on family satisfaction and anxiety. It will be explained that each family will randomly be assigned to two communication pathways, and there will be a short survey for them to complete post-surgery. In the control pathway, the surgeon will communicate with the family per his/her usual practice near the completion of the surgical procedure. In the intervention group, the families will receive additional standardized electronic updates via pagers at three pivotal moments: 1) Initial skin incision has been made, 2) Critical part of the case is completed and closure has begun, 3) Closure is complete, and patient is about to be transferred to the recovery room. A member of the surgical team will be responsible for sending these updates. Then, the surgeon will communicate the final update near the end of the surgical procedure per his/her usual practice.

After the surgery is complete, and both control and intervention groups have received the final update, a research team member will locate the waiting family and administer the post-operative survey rating their satisfaction and anxiety levels using Likert scale questions (1-5 scale). We adopted a previously used survey and modified it accordingly. In addition to the survey, basic demographic information of the patient and family member completing the survey, as well as the number of people in the waiting party, will be reported. When the family member has completed the survey, they will leave the survey in a secure drop box in the waiting area.

To ensure that the results of the survey are reproducible, we will take twenty subjects who completed the survey and ask permission to call them one day after the initial survey. We will then compare the results of the two surveys.

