**Not applicable**

The paper survey will be administered after the final update has been received by the family in the waiting area. A member of the research team will deliver the survey to the family member, and there will be a collection box in the waiting area for the completed surveys. There will be no identifying information on the survey. The survey will be administered only once per family, and it has a total of six questions.

**Statistical Considerations:** Delineate the precise outcomes to be measured and analyzed. Describe how these results will be measured and statistically analyzed. Delineate methods used to estimate the required number of subjects. Describe power calculations if the study involves comparisons. Perform this analysis on each of the primary and secondary objectives, if possible.

We will be examining the relationship between patient families' levels of anxiety and satisfaction with the number of updates received during the perioperative period. We will include a minimum of 96 participants, with 48 cases in each study group. This study sample was chosen using previous data collected in a similar study. Although this study did not administer surgical updates at specific time points, as we propose, they used a similar method of analyzing anxiety and satisfaction levels. Using their mean anxiety ratings, along with the standard deviations, a power analysis revealed that for a power of 0.8 with a significance of 0.05, the proposed study will require a total of 96 participants.

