**Not applicable**

**Number of Subjects:** What is the anticipated number of subjects to be enrolled at UVM/UVM Medical Center and in the case of a multi-center study, with UVM/UVM Medical Center as the lead, the total number of subjects for the entire study.

There will be a minimum of 96 subjects. We anticipate approximately 200, and all subjects will be enrolled at UVM/UVM Medical Center.

**Inclusion/Exclusion Criteria:** Eligibility and ineligibility criteria should be specific. Describe how eligibility will be determined and by whom. Changes to the eligibility criteria at a later phase of the research have the potential to invalidate the research.

Inclusion criteria includes all families of orthopaedic surgical patients of the surgeons involved in this research study. Exclusion criteria include surgeries lasting less than two hours, patients under the age of 18 years old, and non-English speaking patients and/or families. Each orthopaedic surgical case will be reviewed for eligibility prior to the surgery date by a member of the research team.

**Inclusion of Minorities and Women:** Describe efforts to include minorities and women. If either minorities or women are excluded, include a justification for the exclusion.

Women and minorities will be included, given that they meet inclusion criteria listed above.

**Inclusion of Children:** Describe efforts to include children. Inclusion is required unless a clear and compelling rationale shows that inclusion is inappropriate with respect to the health of the subjects or that inclusion is inappropriate for the purpose of the study. If children are included, the description of the plan should include a rationale for selecting or excluding a specific age range of children. When included, the plan must also describe the expertise of the investigative team in working with children, the appropriateness of the available facilities to accommodate children, and the inclusion of a sufficient number of children to contribute to a meaningful analysis relative to the purpose of the study. If children are excluded then provide appropriate justification. Provide target accrual for this population.

Patients under the age of 18 are excluded from this study. Communication with families during the time of surgery is different for pediatric patients than for adult patients. For example, parents are often able to escort children into the operating room.

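### Satisfaction items 2 and 4 define 1 as the lowest answer but print a 0 below it, and the protocol's 1-5 scale leaves out the anxiety answer 0

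*Combined protocol and SAP*

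**What the plan says.** All references are to the combined protocol and SAP.

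- **Survey form, items 2 and 4 (satisfaction).** Both define the scale "with 1 being extremely unsatisfied and 5 being extremely satisfied". The answer row beneath each has six labels, "None at all | Extremely low | Somewhat low | Not high or low | Somewhat high | Extremely high", coded 0, 1, 2, 3, 4, 5.
- **Survey form, item 3 (anxiety).** The same six-answer row, introduced "with 0 being none at all and 5 being extremely high".
- **Second printed copy of the form.** The same wording and codes for all three items.
- **Protocol Summary, Lay Language Summary.** The team will "administer the post-operative survey rating their satisfaction and anxiety levels using Likert scale questions (1-5 scale").
- **Methods and Procedures, Procedures.** The same description: "rating their satisfaction and anxiety levels using Likert scale questions (1-5 scale").
- **Statistical Considerations.** The sample size rests on anxiety ratings from an earlier study: "a power analysis revealed that for a power of 0.8 with a significance of 0.05, the proposed study will require a total of 96 participants". The section gives no scoring range, range check or recoding rule, and names no test or sidedness.

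**The concern.** Satisfaction and anxiety are the study's outcomes, so their codes should have one meaning. For satisfaction they do not: the item wording makes 1 the floor, and the printed row puts another answer beneath it. The labels also differ in kind. The wording runs from dissatisfied to satisfied, whereas the row runs from no amount to a very high amount. Two relatives with the same worst opinion can therefore return different codes.

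For anxiety the form is internally consistent, and the conflict lies between the form and the protocol text. Anyone who took the 1-5 range as the permitted range would treat a defined answer, no anxiety at all, as out of range. If the updates work, that answer should be more common in the intervention arm, so removing it would pull the difference toward zero.

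**Working it through.** **1. The texts side by side**

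| Source | Satisfaction | Anxiety |
|---|---|---|
| Item wording | 1-5 (five codes) | 0-5 (six codes) |
| Printed answer row | 0-5 (six codes) | 0-5 (six codes) |
| Lay Language Summary and Procedures | 1-5 | 1-5 |

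Satisfaction conflicts within the form. Anxiety conflicts only between form and protocol text. Both copies of the form agree, so a text-extraction fault is unlikely.

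**2. The plan's own figure**

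The means and SDs behind 96 are not given, so it cannot be reproduced forward. Solving backward with 48 per arm, two-sided 0.05 (sidedness assumed) and power 0.80: d = (1.960 + 0.842) × √(2/48) = 0.572. Nothing in this point alters that figure.

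**3. Satisfaction: size of the blur (distributions assumed)**

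True opinion is normal, cut at 1.5, 2.5, 3.5 and 4.5 into codes 1-5. A share q of those at the floor circles 0 instead of 1, alike in both arms. If the floor shares are f_c (control) and f_t (intervention), the control mean falls by q × f_c and the difference in means shifts by q × (f_c − f_t).

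| Control mean / SD / effect | f_c | f_t | Difference on 1-5 | Fall in control mean, q = 1 | Shift in difference, q = 1 | Wilcoxon power at 48 per arm, q = 0.5: raw / 0 and 1 pooled |
|---|---|---|---|---|---|---|
| 4.0 / 1.0 / 0.6 | 0.006 | 0.001 | 0.46 | 0.006 | 0.005 | 0.734 / 0.734 |
| 3.5 / 1.2 / 0.7 | 0.048 | 0.012 | 0.58 | 0.048 | 0.036 | 0.752 / 0.752 |
| 3.0 / 1.2 / 0.7 | 0.106 | 0.033 | 0.63 | 0.106 | 0.072 | 0.767 / 0.768 |
| 2.5 / 1.2 / 0.7 | 0.202 | 0.078 | 0.64 | 0.202 | 0.124 | 0.766 / 0.766 |

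Shifts use unrounded shares; powers are from 6,000 simulations. For example, in the last row f_c = Φ((1.5 − 2.5)/1.2) = 0.202 and f_t = Φ((1.5 − 3.2)/1.2) = 0.078. With q = 0.5 the shifts halve. Over q = 0.5 to 1, the control mean falls by 0.00-0.20 and the difference shifts by 0.00-0.12.

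If respondents do distinguish 0 from 1, raw codes do slightly better than pooled ones: 0.769 v 0.767, 0.763 v 0.761, 0.734 v 0.732 and 0.752 v 0.737. Raw ordinal codes are therefore the better main analysis, with pooling as the sensitivity analysis.

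**4. Anxiety: a hypothetical deletion of zeros**

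Assumed: normal with SD 1.2 and control mean 2.5, cut at 0.5, 1.5, ..., 4.5 into codes 0-5; two-sided Welch t test; effect chosen to give power 0.80 at 48 per arm with zeros kept. That needs a shift of 0.715 on the underlying scale.

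- Zeros: control Φ((0.5 − 2.5)/1.2) = 0.048; intervention Φ((0.5 − 1.785)/1.2) = 0.142.
- Zeros kept: means 2.50 and 1.82, SDs 1.20 and 1.17, difference 0.68. SE = √((1.20² + 1.17²)/48) = 0.242; 0.684/0.242 = 2.83; power ≈ Φ(2.83 − 1.99) = 0.80.
- Zeros deleted: means 2.50/0.952 = 2.63 and 1.82/0.858 = 2.12, difference 0.51. SDs are 1.09 and 0.98, with 45.7 and 41.2 answers left. SE = √(1.09²/45.7 + 0.98²/41.2) = 0.222; 0.509/0.222 = 2.29; power ≈ Φ(2.29 − 1.99) = 0.62.
- Zeros recoded to 1 instead: difference 0.59, power 0.78.

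**The case against.** The strongest reply is that the defect does little. Direction and top anchor agree, both arms answer the same form, and a rank comparison of satisfaction is almost unchanged. That stands, and it keeps the point at the low end of minor.

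A reader might infer that the study will lose anxiety data or power. The documents do not support this. The 1-5 range is a parenthesis in two descriptive paragraphs. Statistical Considerations contains no range check or recoding, and item 3 tells the respondent what 0 means, so an analyst holding the form would have to discard a defined answer. Across other assumed SDs (1.2, 1.5) and control means (2.0 to 3.5), power at 48 per arm after deletion would be 0.43 to 0.76. The 0.43 needs about 16% of control and 35% of intervention answers to be zeros, all of them deleted, which is hardly a credible accident. The plan also says of enrolment, "We anticipate approximately 200"; at 100 per arm the case worked above would still have power 0.91 after deletion.

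A reader might also infer that 96 is wrong. It rests on another study's anxiety ratings, and nothing here bears on it.

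Finally, removing the 0 column is only one remedy. If forms have already been collected it would change the response options during the study. That objection stands, and the fix below allows for it.

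What survives is the contradiction: followed as printed, the form gives two codes for one opinion, and the protocol misstates the scale of both outcomes.

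**Conclusion.** Wrong as written; an internal inconsistency at the low end of minor. For satisfaction, the low end and the absolute means are blurred (control mean down 0.00-0.20, difference shifted 0.00-0.12), with almost no effect on ranking the arms. For anxiety there is no loss under anything the plan proposes. The fall from 0.80 to 0.62 is conditional on an unplanned deletion of zeros.

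The contradiction itself is read directly from the documents. Every size given rests on assumed distributions, and the tests and two-sidedness are also assumed, because the plan states none of them.

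**What to change.** - **Items 2 and 4, if no forms have been collected:** make wording and codes agree, using either a 1-5 row labelled from dissatisfied to satisfied, or wording matched to the existing 0-5 row.
- **Items 2 and 4, if enrolment has begun** (the documents do not say): keep the 0-5 codes, correct the wording to match, and record the form version. Analyse the raw codes ordinally, and pool 0 with 1 as a sensitivity analysis.
- **Item 3:** leave as it is.
- **Lay Language Summary and Procedures:** replace the 1-5 description with the scale actually printed for each outcome, and state that an anxiety answer of 0 is valid and kept.
- **Telephone retest:** the amendment says "we will administer the survey via telephone to twenty participants one day after the initial administration of the survey". Have the caller read out every code and label, so that an ambiguous 0 is not mistaken for poor reproducibility.

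The cost is a short survey amendment. The amendment form in the file already changes the survey, so these edits could go with it. The downside is two form versions if enrolment has begun.

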## PURPOSE AND OBJECTIVES

**Purpose:** The importance of the research and the potential knowledge to be gained should be explained in detail. Give background information.

Multiple studies have shown that perioperative communication is important in reducing family member anxiety and improving the overall experience of family members waiting for surgical patients. In fact, perioperative communication and attentiveness have been identified as the two most important determinants of perceived surgeon performance. Moreover, surgeons agree that perioperative communication is important and report feeling as though the patients' family members are pseudo-patients, requiring attention and treatment, and perceive reduced family anxiety as a necessary component toward understanding post-operative status updates and findings.

Communication and empathy is even more important in the case of adverse outcomes. Family members of ICU patients rated attitude, clarity of message, and ability to ask questions as most important when receiving bad news. The CARE/SHARE models of establishing rapport with patients and families suggests it is best to wait until all information is available before speaking with the family, particularly in the event of adverse surgical outcomes. However, presently there is no agreed upon standardized time to deliver post-operative news to patients' families, with some surgeons delivering news before a procedure is entirely complete.

We have identified several times at which different surgeons deliver news in the perioperative period: 1) As soon as the major part of the procedure is completed, 2) While the patient is sutured at the close of the surgery, 3) Once the patient is extubated, and 4) Once all auxiliary information is obtained (x-rays, neurovascular examination, etc.) and the patient is awake. While there is anecdotal evidence that it may be concerning to patients' families to not receive an update at the scheduled ending time of a procedure, actual family preference remains undetermined. In a study by Blum et al, families were surveyed regarding perioperative stress and experience satisfaction. Those receiving periodic updates from a circulating nurse (calling every two hours) reported less anxiety and a better overall experience than the group of families who did not receive periodic updates. However, no study currently exists that examines the optimal timing and level of detail of surgeon-family communication.

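### Survey items 5 and 7 accept contradictory ticks with no coding rule, and item 7 cannot separate the detail of the pages from that of the surgeon's talk

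*Combined protocol and SAP*

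**What the plan says.** The survey (form headed Family Member Demographic Information, reproduced twice in the file) puts two three-box questions to families after surgery.

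- Item 5, on frequency: "Please check all that apply regarding the frequency of updates you received during the perioperative period". The boxes are too frequent, too infrequent, and satisfied.
- Item 7, on detail: "Please check all that apply regarding the amount of detail in the updates you received during the perioperative period". The boxes are too detailed, not detailed enough, and satisfied.
- Item 9, on when to meet the surgeon, instructs instead: "Please select one answer".
- Item 4 is a rating on a printed 0 to 5 scale: "Please rate your level of satisfaction with the number of updates provided during the perioperative period".

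Under Methods and Procedures, families are randomised to two pathways. For control: "In the control pathway, the surgeon will communicate with the family per his/her usual practice near the completion of the surgical procedure". Families allocated to the pager arm get more than this: "the families will receive additional standardized electronic updates via pagers at three pivotal moments". After the pages comes the same usual contact: "Then, the surgeon will communicate the final update near the end of the surgical procedure per his/her usual practice".

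The Purpose section justifies the study partly by saying that "no study currently exists that examines the optimal timing and level of detail of surgeon-family communication". Statistical Considerations names anxiety and satisfaction with the number of updates. It gives no coding or analysis rule for item 5 or item 7.

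**The concern.** There are two separate weaknesses.

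First, the response format. Too much, too little and satisfied conflict with one another, yet the instruction invites more than one tick. Item 9 shows that the authors used single choice where they wanted one answer. Without a rule, any multiple tick has to be recoded or dropped after the data are in hand, and the form also records the study group. The planned telephone retest of twenty participants meets the same problem: agreement on these two items has no defined meaning while such patterns are uncoded.

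Second, what item 7 rates. It asks about all updates as one lump. Intervention families have two sources, pages and surgeon. A family that found the pages thin and the talk complete cannot say so clearly. If it ticks both boxes, an analyst cannot tell a considered mixed answer from a slip. At stake is a usable answer about the pages' level of detail, which is one of the two gaps the protocol names.

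**Working it through.** **1. Tick patterns.** Input: three boxes per item, each ticked or not (survey items 5 and 7). Number of patterns = 2^3 = 8.

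| Pattern | Count |
|---|---|
| Blank | 1 |
| One box | 3 |
| Two boxes | 3 |
| All three | 1 |

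Multiple ticks = 3 + 1 = 4. The pairs are too much with too little, too much with satisfied, and too little with satisfied. None of the four can be placed in a single category, and no rule in the protocol covers them. This counts what the form permits and does not estimate how often it will happen.

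**2. What each arm rates in item 7.**

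| Arm | Updates covered by the one answer |
|---|---|
| Control | Surgeon's usual communication |
| Intervention | Three standardised pages and the surgeon's usual communication |

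Allocation is random, so a difference between arms in the item 7 answer estimates the effect of adding pages on the rating of everything received. The intervention arm's answer cannot be split into a part for the pages and a part for the talk. No other structured item asks about detail; item 11 is free text.

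**3. Does this touch the sample size?** The plan states 96 in total, 48 per group, power 0.8, significance 0.05, based on mean anxiety ratings from a cited earlier study. The means and standard deviations are not given, so 96 cannot be reproduced directly. Solving backwards (two-sided, normal approximation):

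d = (1.960 + 0.842) × √(2/48) = 0.572

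A standardised difference of 0.575 returns 96. Neither item 5 nor item 7 enters this calculation.

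**4. What unusable answers could cost (illustration only).** Assumptions: satisfied is analysed as yes or no, with 60% in control and 85% in intervention, two-sided 0.05, and unusable forms spread equally over the arms. None of these rates is in the documents.

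Power = Φ{[|p2 − p1| − 1.96√(2p̄(1 − p̄)/n)] / √[(p1(1 − p1) + p2(1 − p2))/n]}, with p̄ = 0.725.

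For n = 48: (0.25 − 1.96 × 0.0911)/0.0875 = 0.815, giving power 0.793.

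| Unusable | n per arm | Power |
|---|---|---|
| 0% | 48 | 0.793 |
| 5% | 45.6 | 0.771 |
| 10% | 43.2 | 0.748 |
| 20% | 38.4 | 0.696 |

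The loss is about 2 to 10 percentage points over this range (0.793 − 0.771 = 0.022; 0.793 − 0.696 = 0.097). The comparison loses precision but stays readable.

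**The case against.** The strongest reply is that these are exploratory items. The stated objective is the effect on satisfaction, anxiety and overall experience. No arm varies the level of detail, and the statistical section names neither item. A mixed tick may also be an honest mixed view, so not every multiple tick is an error. All of this stands, and it keeps the point small. It does not supply a coding rule, and it does not let anyone tell a mixed view from a mistake.

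A reader might infer something stronger: that items 5 and 7 are the only measures of frequency and detail, and that they cannot be read as an effect of the pages because the arms rate different things. The documents do not support this, for two reasons.

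- Item 4 also measures satisfaction with the number of updates, in both arms, and that is the quantity Statistical Considerations names. What item 5 adds is direction, too many or too few.
- The different set of updates in each arm is the randomised intervention itself. A between-arm difference in the rating of all updates is a valid estimate of the effect of adding pages to usual communication.

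Nor does item 5 need a box for having received no updates. A control family that heard nothing before the surgeon came can tick too infrequent if it minded and satisfied if it did not.

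**Conclusion.** The point holds as a cheap improvement to the questionnaire. Items 5 and 7 allow 4 of 8 patterns that cannot be assigned to one category, and the protocol has no rule for them. Item 7, the only structured measure of detail, supports a randomised comparison of overall satisfaction with detail but cannot show whether the pages themselves carry the right detail. The anxiety comparison, the satisfaction comparisons (item 4 included) and the sample size are unaffected.

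The pattern count and the inability to separate pages from talk follow from the form and the procedures alone. The practical size of the tick problem depends on how often families tick more than one box, which the documents do not give; the power figures above rest on assumed rates.

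**What to change.** In both copies of the form:

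1. Change items 5 and 7 to the single-answer instruction already used in item 9.
2. Keep item 7 as the overall rating and compare it between arms. Replacing it with separate page and talk items would lose the randomised comparison of overall detail.
3. Add one item on the detail of the pager messages and report it descriptively in the intervention arm only; it has no comparator in control. If both arms use the same form, give the item a not-applicable box.
4. Do not add a no-updates option to item 5. In a single-choice item it would replace control families' opinions with a fact about exposure that the Group field largely records already.

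For forms already completed, write down a coding rule for multiple ticks before looking at results by arm. One workable rule is to hold them as a separate mixed category and report their number in each arm. The same rule should govern the retest comparison.

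The cost is one extra line on a survey that is already being amended. The downside is that multi-tick answers on earlier forms cannot be pooled directly with the revised items, so the form version should be recorded.
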